| Hyperthyroidism, Grade 3 | 
 • Hold MGC018 • Consider hospitalization and consulting endocrinologist • Begin IV corticosteroids such as methylprednisolone 2 to 4 mg/kg IV (or equivalent) divided twice daily. • Initiate hormonal replacement therapy as necessary • Consider restarting MGC018 with complete resolution or stable on hormone replacement therapy within 28 days and if corticosteroid dose is reduced to ≤ 10 mg prednisone or equivalent per day. • On resuming MGC018, reduce dose by one dose level after first and second occurrences • Discontinue MGC018 after third occurrence |
| Hyperthyroidism, Grade 4 | 
 • Treat as grade 3 • On resuming MGC018 reduce dose by two dose levels after first occurrence • Discontinue MGC018 after second occurrence |

| Event | Management |
|--------------------------|---|
| Hypophysitis, Grade 1 | 
 • No specific therapy required • Continue MGC018 |
| Hypophysitis, | 
 • Hold MGC018 |

| | |
|----------------|--|
| Grade \geq 2 | 
 • Consult endocrinologist • Consider hospitalization • Consider short course of high dose IV corticosteroids e.g. methylprednisolone 2 to 4 mg/kg/day or equivalent divided twice daily. • Initiate hormonal replacement as indicated • Study drug may be resumed as allowed by protocol when: 
 • Endocrinopathy is controlled with appropriate replacement therapy • Corticosteroid dose reduced to \leq 10 mg prednisone or equivalent per day. • Brain MRI recommended |
|----------------|--|

MRI = magnetic resonance imaging

OCULAR EVENTS

Ocular toxicity, including, but not limited to, dry eye, photophobia or blurry vision have been observed in participants treated with antibody drug conjugates, and could occur at any time during treatment with MGC018. Management guidelines for ocular events are provided in Table 12.

Table 12. Management Guidelines for Blepharitis

| Event | Management |
|----------------------|---|
| Blepharitis, Grade 1 | 
 No specific therapy required. Daily cleansing with warm, clean cloth. Apply lubricating eye drops Patient referral to ophthalmologist is strongly recommended. Initiate treatment with topical corticosteroid eye drops and topical immunosuppressive therapy. If symptoms persist, treat as a Grade 2 event. |
| Blepharitis, Grade 2 | 
 Hold MGC018 Consider topical/ocular corticosteroids, antihistamine, artificial tears Resume MGC018 if resolved to \leq grade 1 within 28 days and discontinue MGC018 if symptoms last > 28 days On resuming MGC018, if symptoms lasted > 14 days, reduce dose by one dose level |
| Blepharitis, Grade 3 | 
 Hold MGC018 Consider referral to ophthalmologist. Consider topical/ocular and/or systemic corticosteroids Resume MGC018 if resolved to \leq grade 1 within 28 days and discontinue MGC018 if symptoms last > 28 days On resuming MGC018, reduce dose by one dose level |
| Blepharitis, Grade 4 | 
 Permanently discontinue MGC018 Consult ophthalmology within 24 hours Treat as for grade 3 and as appropriate for life-threatening symptoms |

HEMATOLOGIC EVENTS

Blood counts should be monitored to determine if dose modification is needed. Consider monitoring CBC bi-weekly or weekly based on the participant's medical history and incidence of myelosuppressive AE's during study drug administration.

Blood counts will be performed in case of fever (a measured temperature of 100.4 F or greater) or evidence of infection. Neutropenic complications should be managed promptly with antibiotic support and use of G-CSF according to current ASCO guidelines for use of white blood cell growth factors.

Consider transfusion of platelets for thrombocytopenia. Use of anticoagulants and platelet inhibitors should be held until thrombocytopenia resolves.

Anemia should be evaluated and treated for other underlying etiology e.g. iron or vitamin B12 deficiency, bleeding, and renal insufficiency. Consider transfusion of red blood cells or whole blood for

anemia. Caution is recommended in patients with \geq grade 2 anemia, with appropriate measures taken as clinically indicated. Patients will be supported appropriately by the treating physician.

No specific treatment or drug holds are required for lymphopenia, regardless of CTCAE grade, unless associated with opportunistic infection. If the patient develops an opportunistic infection with concurrent lymphopenia, MGC018 should be delayed until resolution of lymphopenia and the opportunistic infection

Management guidelines for hematologic events are provided in Table 13.

Table 13. Management Guidelines for Hematologic Events

| Event | Management |
|------------------------------|--|
| Neutropenia, Grade 1 or 2 | 
 • No specific therapy required • MGC018 should not be given to participants with neutrophil counts ≤ 1500 cells/mm³ • Consider dose reduction of MGC018 |
| Neutropenia, Grade 3 | 
 • Hold MGC018 until recovery to \leq grade 1 • Monitor neutrophil counts weekly until recovery to \leq grade 1 • Discontinue MGC018 if not recovered to \leq grade 1, within 21 days • Restart MGC018 if recovered to \leq grade 1 within 21 days. • On resuming MGC018, reduce dose by one dose level after first and second occurrences • Discontinue MGC018 after third occurrence |
| Neutropenia, Grade 4 | 
 • Hold MGC018 until recovery to \leq grade 1 • Monitor neutrophil counts weekly until recovery to \leq grade 1 • Discontinue MGC018 if not recovered to \leq grade 1, within 21 days • Restart MGC018 at one or two level dose reduction if recovered to \leq grade 1 within 21 days. • On resuming MGC018 reduce dose by two dose levels after first occurrence • Discontinue MGC018 after second occurrence |
| Thrombocytopenia, Grade 1 | 
 • No specific therapy required • Consider dose reduction of MGC018 |

| | |
|-----------------------------------|--|
| Thrombocytopenia, Grade 2 or 3 | 
 • Hold MGC018 until recovery to \leq grade 1 • Monitor platelet counts weekly until recovery to \leq grade 1 • Restart MGC018 with one level dose reduction if recovered to \leq grade 1 • Reduce dose by one dose level on resumption after second and third occurrences • Discontinue MGC018 after fourth occurrence • Discontinue MGC018 if not recovered to \leq grade 1 within 21 days. |
| Thrombocytopenia, Grade 4 | 
 • Hold MGC018 until recovery to \leq grade 1 • Monitor platelet counts weekly until recovery to \leq grade 1 • Restart MGC018 with one or two level dose reduction if recovered to \leq grade 1 • Discontinue MGC018 if not recovered to \leq grade 1 within 21 days. • On resuming MGC018 reduce dose by two dose levels after first occurrence • Discontinue MGC018 after second occurrence |
| Anemia, Grade 1 | 
 • No specific therapy required |
| Anemia, Grade 2 | 
 • Consider iron replacement therapy, erythropoiesis stimulating agent |
| Anemia, Grade 3 | 
 • Consider iron replacement therapy, erythropoiesis stimulating agent • Consider transfusion if symptomatic • Consider holding MGC018 until recovery to \leq grade 2 • Dose reduction of one dose level for ≥ 2 events of grade 3 anemia • Discontinue MGC018 after fourth occurrence |
| Anemia, Grade 4 | 
 • Transfuse with whole blood or packed red blood cells • Permanently discontinue MGC018 for grade 4 anemia that persists despite intervention. |

PLEURAL AND PERICARDIAL EFFUSIONS

Supportive care per institutional practice should be used to manage pleural and pericardial effusions. For pleural and pericardial effusions consider a dose delay and/or dose reduction.

Management guidelines for pleural effusions are provided in Table 14. Management guidelines for pericardial effusions are provided in Table 15.

Table 14. Management Guidelines for Pleural Effusions

| Event | Management |
|------------------------------|---|
| Pleural effusion, Grade 1 | 
• No specific therapy required• Close monitoring of cardiac and lung function and imaging• Consider diuretics |
| Pleural Effusion, Grade 2 | 
• Hold MGC018• Consider diuretics or therapeutic thoracentesis• Consider corticosteroids: 1 to 2 mg/kg or oral prednisone or equivalent per day divided twice daily. Taper corticosteroids over 4 weeks or as clinically indicated• Resume MGC018 with a one level dose reduction at next scheduled dose if pleural effusion resolves to \leq grade 1 within 21 days. If pleural effusion grade 2 recurs further reduce dose by one dose level. |
| Pleural Effusion, Grade 3 | 
• Hold MGC 018• Therapeutic thoracentesis• Consider corticosteroids: 1 to 2 mg/kg or oral prednisone or equivalent per day divided twice daily. Taper corticosteroids over 4 weeks or as clinically indicated.• Resume MGC018 with a one level dose reduction at next scheduled dose if pleural effusion resolves to \leq grade 1 within 21 days. If pleural effusion grade 3 recurs further reduce dose by one dose level. |
| Pleural Effusion, Grade 4 | 
• Permanently discontinue MGC018• Recommend hospitalization with pulmonary consultation and diagnostic evaluation including chest X-ray and CT scan.• Initiate maximal supportive care including IV corticosteroids. Continue IV methylprednisolone 2 mg/kg/day for 5 days then switch to oral prednisolone 1 mg/kg/day x 3 days, then reduce to 60 mg/day prednisolone. Reduce prednisolone dose by 10 mg every 5-7 days (as toxicity allows) until dose is 10 mg/day. Once steroid dose is 10 mg/day, reduce by 5 mg every 5-7 days then stop. High doses may be used in consultation with the sponsor's medical monitor. |

Table 15. Management Guidelines for Pericardial Effusions

| Event | Management |
|-------------------------------|--|
| Pericardial Effusion, Grade 1 | 
 • No specific therapy required • Continue MGC018 |
| Pericardial Effusion, Grade 2 | 
 • Hold MGC018 • Consider diuretics • Consider corticosteroids: 1 to 2 mg/kg of oral prednisone or equivalent per day divided twice daily. Taper corticosteroids over 4 weeks or as clinically indicated • Resume MGC018 at next scheduled dose with a one level dose reduction if pericardial effusion resolves to \leq grade 1 within 21 days. If pericardial effusion grade 2 recurs further dose reduce by one level. |
| Pericardial Effusion, Grade 3 | 
 • Hold MGC018 • Consider pericardiocentesis. • Consider corticosteroids: 1 to 2 mg/kg of oral prednisone or equivalent per day divided twice daily. Taper corticosteroids over 4 weeks or as clinically indicated. • Resume MGC018 at next scheduled dose with a one level dose reduction if pericardial effusion resolves to \leq grade 1 within 21 days. If pericardial effusion grade 3 recurs further reduce dose by one dose level. |
| Pericardial Effusion, Grade 4 | 
 • Permanently discontinue MGC018 • Hospitalize, consider pericardiocentesis • Recommend cardiology consult/diagnostic evaluation including echocardiogram • Initiate maximal supportive care including IV corticosteroids. Continue IV methylprednisolone 2 mg/kg/day for 5 days then switch to oral prednisolone 1 mg/kg/day x 3 days, then reduce to 60 mg/day prednisolone. Reduce prednisolone dose by 10 mg every 5-7 days (as toxicity allows) until dose is 10 mg/day. Once steroid dose is 10 mg/day, reduce by 5 mg every 5-7 days then stop. High doses may be used in consultation with the sponsor's medical monitor. |

NERVOUS SYSTEM EVENTS

Management guidelines for patients experiencing nervous system toxicity are provided in Table 16.

Table 16. Management Guidelines for Nervous System Events

| Event | Management |
|--------------|---|
| Grade 1 | 
• No specific therapy required, close monitoring of neuropathy |
| Grade 2 | 
• Hold MGC018• Consider neurology consultation• Consider corticosteroids: 1 to 2 mg/kg of oral prednisone or equivalent per day divided twice daily. Taper corticosteroids over 4 weeks or as clinically indicated.• Resume MGC018 at next scheduled dose if symptoms resolve to \leq grade 1 within 21 days with or without treatment. |
| Grade 3 or 4 | 
• Permanently discontinue MGC018• Consider hospitalization and neurology consultation• Begin corticosteroids 2 to 4 mg/kg of oral or IV methylprednisolone or equivalent per day divided twice daily. Continue IV methylprednisolone 2 mg/kg/day for a total of 5 days then switch to oral prednisolone 1 mg/kg/day x 3 days, then reduce to 60 mg/day prednisolone. Reduce prednisolone dose by 10 mg every 7 days (as toxicity allows) until dose is 10 mg/day. Once steroid dose is 10 mg/day, reduce by 5 mg every 5-7 days then stop |

CARDIOVASCULAR EVENTS

Management guidelines for patients experiencing cardiovascular toxicity are provided in Table 17.

Table 17. Management Guidelines for Cardiovascular System Events

| Event | Management |
|--------------|--|
| Grade 1 | 
 No specific therapy required; close monitoring |
| Grade 2 | 
 Permanently discontinue MGC018 for patients who experience grade 2 myocarditis Consider cardiology consultation. Evaluate cardiac biomarkers e.g. creatine kinase, troponin, and beta-natriuretic peptide. Echocardiogram and CT imaging if clinically indicated. Consider corticosteroids: 1 to 2 mg/kg of oral prednisone or equivalent per day divided twice daily. Taper corticosteroids over 4 weeks or as clinically indicated. |
| Grade 3 or 4 | 
 Permanently discontinue MGC018 Consider hospitalization and cardiology consultation Consider obtaining cardiac biomarkers e.g. creatine kinase, troponin, and beta-natriuretic peptide. Echocardiogram and CT imaging if clinically indicated. Begin corticosteroids 2 to 4 mg/kg of oral or IV methylprednisolone or equivalent per day divided twice daily. Continue IV methylprednisolone 2 mg/kg/day for a total of 5 days then switch to oral prednisolone 1 mg/kg/day x 3 days, then reduce to 60 mg/day prednisolone. Reduce prednisolone dose by 10 mg every 5-7 days (as toxicity allows) until dose is 10 mg/day. Once steroid dose is 10 mg/day, reduce by 5 mg every 5-7 days then stop. Consider infliximab |

MUSCULOSKELETAL TOXICITY

Management guidelines for patients experiencing musculoskeletal toxicity are provided in Table 18.

Table 18. Management Guidelines for Musculoskeletal Events

| Event | Management |
|---------|--|
| Grade 1 | 
 No specific therapy required, close monitoring Consider anti-inflammatory medication e.g. ibuprofen |
| Grade 2 | 
 Hold MGC018 Consider rheumatology consultation Consider corticosteroids: 1 to 2 mg/kg of oral prednisone or equivalent per day divided twice daily. Taper corticosteroids over 4 weeks or as clinically indicated. |

| | |
|---------|--|
| | 
 • Resume MGC018 at next scheduled dose if symptoms resolve to \leq grade 1 within 21 days with or without treatment. • No dose reduction required after first occurrence • On resuming MGC018, reduce dose by one dose level after second and third occurrences • Discontinue MGC018 after fourth occurrence |
| Grade 3 | 
 • Hold or permanently discontinue MGC018 • Consider hospitalization and rheumatology consultation • Begin corticosteroids 2 to 4 mg/kg of oral or IV methylprednisolone or equivalent per day divided twice daily. Continue IV methylprednisolone 2 mg/kg/day for a total of 5 days then switch to oral prednisolone 1 mg/kg/day x 3 days, then reduce to 60 mg/day prednisolone. Reduce prednisolone dose by 10 mg every 5-7 days (as toxicity allows) until dose is 10 mg/day. Once steroid dose is 10 mg/day, reduce by 5 mg every 5-7 days then stop. • Consider infliximab • If not responding within 14 days, consider use of disease modifying antirheumatic drugs e.g. sulfazine, methotrexate. • On resuming MGC018, reduce dose by one dose level after first and second occurrences • Discontinue MGC018 after third occurrence |
| Grade 4 | 
 • Treat as grade 3 • On resuming MGC018 reduce dose by two dose levels after first occurrence • Discontinue MGC018 after second occurrence |

INFUSION-RELATED REACTIONS

Premedications at least 30 minutes prior to each infusion of MGC018 include: acetaminophen 650 to 1000 mg PO or ibuprofen 400 mg PO, diphenhydramine 50 mg PO or IV or equivalent H1 antagonist, famotidine 40 mg PO or 20 mg IV or equivalent H2 antagonist, corticosteroid (e.g dexamethasone 4 mg IV or equivalent).

For subsequent administration of MGC018, participants who had infusion reactions that were not adequately or only moderately controlled, other medications may also be considered as part of the pre-medication regimen for subsequent doses.

Guidelines for medical management of IRRs during Cycle 1 are provided in Table 19. For subsequent cycles, IRRs should be managed according to institutional guidelines.

Table 19. Management Guidelines for Infusion-Related Reactions

| Event | Management |
|-------------------|--|
| IRR, Grade 1 | 
 • Reduce infusion rate to half the rate being given at the time of event onset. • Monitor the participant for worsening of condition • After the event has resolved, the sponsor-investigator should wait for 30 minutes while delivering the infusion at the reduced rate. • If the infusion is tolerated at the reduced rate for 30 minutes after symptoms have resolved, the infusion rate may be increased to the original rate. • Prophylactic premedication with antipyretics, antihistamines, and/or analgesics should be given prior to all subsequent infusions |
| IRR, Grade 2 | 
 • Interrupt infusion. • Administer aggressive symptomatic treatment (e.g., oral or IV antihistamine, anti-pyretic medication, glucocorticoids, epinephrine, bronchodilators, oxygen, IV fluids). • After symptoms have resolved to baseline or decreased to grade 1, resume infusion at half the rate being given at the time of event onset. • If the infusion is tolerated at reduced rate for 30 minutes, rate may be escalated to original rate after 30 minutes as tolerated • For subsequent infusions, prophylactic administration of premedication with antihistamines, anti-pyretics, and/or analgesics and monitor closely for IRRs. Corticosteroids may also be added (dexamethasone 10 mg IV or hydrocortisone 25 to 100 mg IV or higher) |
| IRR, Grade 3 or 4 | 
 • Stop infusion. Do not flush tubing. • Administer aggressive symptomatic treatment (e.g., oral or IV antihistamine, anti-pyretic medication, glucocorticoids, epinephrine, bronchodilators, oxygen, IV fluids). • If grade 3 infusion reaction occurs, discontinue treatment for that day. If symptoms have resolved to baseline within 12 hours, MGC018 may be infused the next day with premedication and for any subsequent doses with antipyretics, antihistamines, and corticosteroids. • Participants who have a grade 3 infusion reaction that does not resolve within 12 hours should not receive further treatment with MGC018. • Participants who experience a second grade 3 infusion reaction at time of rechallenge with MGC018 will permanently discontinue treatment with study drugs. • Participants who have a grade 4 infusion reaction will not receive further treatment with MGC018 • Reports as an IRE within 24 hours and event as SAE |

IRR = infusion-related reaction, IRE=infusion related event, SAE=serious adverse event

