4.2.3.2 Guidelines for management of suspected MGC018-related toxicities

Criteria for treatment modification and guidelines for the management of toxicities are summarized below. Generally, temporary suspension of MGC018 must occur if a patient experiences a serious adverse event or a grade 3 or 4 non-serious adverse event assessed by the investigator as related to MGC018. If the event resolves to grade ≤ 1 , MGC018 may be restarted at the same dose level. If MGC018 is delayed due to toxicity for > 8 weeks beyond when the next dose should have been given, the patient must be permanently discontinued from MGC018.

PULMONARY EVENTS

Immune-mediated pulmonary events are a potential risk with MGC018. Patients will be assessed for pulmonary signs and symptoms throughout the study and will have computed tomography (CT) scans of the chest performed at every tumor assessment.

All pulmonary events should be thoroughly evaluated for other commonly reported etiologies such as pneumonia or other infection, lymphangitic carcinomatosis, pulmonary embolism, heart failure, chronic obstructive pulmonary disease, or pulmonary hypertension. Management guidelines for pulmonary events are provided in Table 5.

Table 5. Management Guidelines for Pneumonitis

| Event | Management |
|--------------|---|
| Grade 1 | 
 • Continue MGC018 and monitor closely. • Re-evaluate on serial imaging. • No specific therapy required |
| Grade 2 | 
 • Hold MGC018 • Consider treatment with corticosteroids equivalent to 1–2 mg/kg/day oral prednisone or equivalent divided twice daily • Taper corticosteroids over 4 weeks or as clinically indicated • Resume MGC018 administration at next scheduled dose if pneumonitis resolves to grade 1 or baseline within 5 days with or without treatment. On resuming MGC018, reduce dose by one dose level. • Discontinue MGC018 after second occurrence |
| Grade 3 or 4 | 
 • Permanently discontinue MGC018 • Hospitalize • Referral for pulmonary consult with diagnostic evaluation with chest X-ray and CT scan. • Initiate treatment with IV corticosteroids, suggest methylprednisolone at 2 to 4 mg/kg/day divided twice daily. Higher doses may be used in consultation with the sponsor's medical monitor. • If event does not improve within 3 to 5 days after initiating corticosteroids, consider adding an immunomodulatory agent. |

HEPATIC EVENTS

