For palmar-plantar erythrodysesthesia, hold MGC018 until toxicity resolves to \leq grade 1. MGC018 may be resumed with MGC018 decrease of one dose level. Discontinue MGC018 if patient does not recover to \leq grade 1 within 28 days.

Table 9. Management Guidelines for Dermatologic Events

| Event | Management |
|-------|------------|
|-------|------------|

| | |
|-----------------------------|---|
| Dermatologic event, Grade 1 | 
 • For dry skin, consider application of moisturizers as needed to affected area • Symptomatic treatment with low dose topical corticosteroids (betamethasone 0.1% or hydrocortisone 1%) or antihistamines • Persistent grade 1 or 2 rash should be managed with higher dose topical corticosteroids and/or oral prednisone (1 to 2 mg/kg/day) if there is not improvement with topical therapies or the rash is associated with other dermal toxicities such as pruritis. • Evaluate for use of concomitant medications and herbal supplements that may exacerbate skin toxicity. |
| Dermatologic event, Grade 2 | 
 • Treat as grade 1 • No dose reduction required after first occurrence • On resuming MGC018, reduce dose by one dose level after second and third occurrences • Discontinue MGC018 after fourth occurrence |
| Dermatologic event, Grade 3 | 
 • Hold MGC018 • Initiate oral corticosteroids (oral prednisone 1 to 2 mg/kg/day) • Evaluate participant use of concomitant medications and herbal supplements that may exacerbate skin toxicity • Consider obtaining skin biopsy if SJS or TEN is suspected. If possible, refer to specialized care center for clinical management. Cyclosporine and/or IV immunoglobulin may be considered for management of SJS or TEN. • Resume MGC018 at next scheduled dose if: • Skin toxicity resolves to \leq grade 1 or baseline within 21 days with maximal supportive care • Discontinue study drugs if skin toxicity does not resolve to \leq grade 1 or baseline within 21 days, or for any grade SJS or TEN of any duration. • On resuming MGC018, reduce dose by one dose level after first and second occurrences • Discontinue MGC018 after third occurrence |

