| Dermatologic event, Grade 4 | 
 • Initiate oral corticosteroids (oral prednisone 1 to 2 mg/kg/day) • Evaluate patient for use of concomitant medications or herbal supplements that may exacerbate skin toxicity • Consider obtaining a skin biopsy if possible diagnosis of SJS or TEN. If possible, refer to specialized care center for clinical management. Cyclosporine and/or IV immunoglobulin may be considered for management of SJS or TEN. |

| | |
|--|---|
| | 
 • Consideration should be given to start IV corticosteroids (methylprednisolone 1 to 2 mg/kg/day) for grade 4 dermatologic toxicities with tapering on resolution to <grade 2 over 30 days. • If SJS or TEN are confirmed, permanently discontinue MGC018 • On resuming MGC018 reduce dose by two dose levels after first occurrence • Discontinue MGC018 after second occurrence |
|--|---|

SJS=Stevens-Johnson Syndrome, TEN=toxic epidermal necrolysis

RENAL EVENTS

Immune-related nephritis is a potential risk with MGC018. Eligible patients must have adequate renal function. Renal function, including serum creatinine, should be monitored throughout study treatment. Patients with abnormal renal function should be evaluated and treated for other more common etiologies (including prerenal and postrenal causes, and concomitant medications such as non-steroidal anti-inflammatory drugs).

Patients with signs and symptoms of nephritis, in the absence of an identified alternate etiology, should be treated according to the guidelines in Table 10.

Table 10. Management Guidelines for Nephritis

| Event | Management |
|--------------------|---|
| Nephritis, Grade 1 | 
 • Continue MGC018 • No specific therapy required • Close monitoring of renal function |
| Nephritis, Grade 2 | 
 • Hold MGC018 • Consider nephrology consultation and renal biopsy to confirm interstitial nephritis. • Consider initiating treatment with corticosteroids equivalent to 1–2 mg/kg/day oral prednisone per day, dose divided twice daily. • Taper corticosteroids over 4 weeks or as clinically indicated. • Resume MGC018 at next scheduled dose if nephritis resolves to \leq grade 1 within 21 days with or without treatment • No dose reduction required after first occurrence • On resuming MGC018, reduce dose by one dose level after second and third occurrences • Discontinue MGC018 after fourth occurrence |

| | |

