5.2.3 Adverse events of special interest (AESIs)

AESIs are a subset of events to monitor of scientific and medical concern specific to the product, for which ongoing monitoring and rapid communication by the Investigator to the study sponsor is required (no more than 24 hours after learning of the event). Such an event might require further investigation in order to characterize and understand it. Depending on the nature of the event, rapid communication by the trial sponsor to other parties (e.g., Regulatory Authorities; MacroGenics) may also be warranted.

AESIs for this study include the following:

- Cases of potential drug-induced liver injury that include an elevated ALT or AST in combination with either an elevated bilirubin or clinical jaundice, as defined by Hy's law:
Treatment-emergent ALT or AST $> 3 \times$ ULN in combination with total bilirubin $> 2 \times$ ULN
Treatment-emergent ALT or AST $> 3 \times$ ULN in combination with clinical jaundice
- Grade 3 or higher pneumonitis
- Grade 3 or higher pleural and/or pericardial effusion
- Grade 3 or higher ocular toxicities (e.g., uveitis, retinitis, optic neuritis)
- Severe cutaneous reactions (e.g., Stevens-Johnson syndrome, dermatitis bullous, toxic epidermal necrolysis)

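### Table 9 stops a slow-recovering grade 3 skin event at 21 days but sets no such stop for a first grade 4 skin event, which may be re-treated after a longer recovery

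*Combined protocol and SAP*

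**What the plan says.** All of this is in section 4.2.3.2 of the combined protocol and SAP unless another section is named.

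- **Table 9, grade 3.** Hold MGC018. Resume only if the event resolves to grade 1 or less, or baseline, within 21 days. The stop is mandatory: "Discontinue study drugs if skin toxicity does not resolve to" (at most) "grade 1 or baseline within 21 days, or for any grade SJS or TEN of any duration".
- **Table 9, grade 4.** Steroids, a review of concomitant medication and a possible skin biopsy. If IV steroids are used, the taper is described as "for grade 4 dermatologic toxicities with tapering on resolution to <grade 2 over 30 days". The row's stops are "If SJS or TEN are confirmed, permanently discontinue MGC018" and a second occurrence. Restarting is foreseen: "On resuming MGC018 reduce dose by two dose levels after first occurrence". The row contains no hold, no recovery grade, no time limit and no instruction to manage the event as grade 3.
- **General rule at the start of 4.2.3.2.** For events judged related to MGC018, "temporary suspension of MGC018 must occur if a patient experiences a serious adverse event or a grade 3 or 4 non-serious adverse event". Restart is allowed once the event is grade 1 or less. Treatment ends for good if the delay exceeds 8 weeks past the date on which the next dose was due.
- **Palmar-plantar erythrodysesthesia.** It has its own rule above Table 9, starting "For palmar-plantar erythrodysesthesia, hold MGC018 until toxicity resolves to", with a 28-day stop at any grade.
- **Table 4 (section 4.2.3.1).** There are three dose levels: 2.0, 1.5 and 1.0 mg/kg every 4 weeks.

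**The concern.** A stopping rule for toxicity should not become more permissive as the event becomes more severe. Read row by row, Table 9 does that for recovery time. A grade 3 event that takes longer than 21 days to resolve ends treatment. A first grade 4 event with the same time course need not, unless it is Stevens-Johnson syndrome (SJS), toxic epidermal necrolysis (TEN) or palmar-plantar erythrodysesthesia.

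What is at stake is whether a patient who recovered slowly from a life-threatening skin event is exposed to the drug again. Section 5.1.1 lists severe cutaneous reactions among the known risks of MGC018. The list of events of special interest in 5.2.3 names one that is neither SJS nor TEN: "Severe cutaneous reactions (e.g., Stevens-Johnson syndrome, dermatitis bullous, toxic epidermal necrolysis". That list creates a duty to report quickly, not a duty to stop.

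**Working it through.** The plan states no figure for the resulting window, so there is none to reproduce. The check sets the two rows side by side and then works out the dates.

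| | Skin grade 3 | Skin grade 4, first event |
|---|---|---|
| Hold | Stated in the row | Only through the general rule |
| Recovery needed to restart | Grade 1 or less, or baseline (row) | Grade 1 or less (general rule) |
| Mandatory stop for slow recovery | 21 days (row) | More than 8 weeks past the due dose (general rule) |
| Stop for SJS/TEN | Any grade | If confirmed |
| Dose on restart | One level lower | Two levels lower |

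**Which patients.** A two-level reduction exists in Table 4 only from 2.0 mg/kg: 2.0 to 1.5 to 1.0. A patient already at 1.5 or 1.0 mg/kg has no level two steps below, and the plan does not say what happens then. The comparison is therefore made only for patients still at 2.0 mg/kg, who would restart at 1.0 mg/kg.

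**Inputs.** Cycle length 28 days (4.2.2.1); grade 3 limit 21 days (Table 9); general limit 8 weeks = 8 × 7 = 56 days past the due dose (4.2.3.2). The plan does not say when the 21 days start, so both natural choices are shown.

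**Clock from onset.** Latest permitted restart = days from onset to the due dose + 56.

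| Onset | Latest restart after onset | Excess over 21 days |
|---|---|---|
| Dosing day (cycle day 1) | 28 + 56 = 84 days | 84 − 21 = 63 days |
| Cycle day 15 | 14 + 56 = 70 days | 70 − 21 = 49 days |
| Cycle day 28 | 1 + 56 = 57 days | 57 − 21 = 36 days |
| Due day, before infusion | 0 + 56 = 56 days | 56 − 21 = 35 days |

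**Both clocks from the due dose.** 56 − 21 = 35 days.

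Under either clock the grade 4 window is at least 35 days longer.

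**Would a 21-day limit collide with the grade 4 steroid taper?** The 30-day taper begins on resolution. Resolution on day 21 plus a full taper ends on day 21 + 30 = 51. That is 56 − 51 = 5 to 84 − 51 = 33 days before the general limit counted from onset, and 5 days before it if both clocks start at the due dose. The limit and the taper are compatible.

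**The case against.** The strongest reply is that the grade 3 stop already covers grade 4. Its sentence speaks of skin toxicity in general and mentions SJS and TEN of any grade, so a clinician could well apply it to a worse event. But the any-grade wording belongs only to the SJS/TEN part. The 21-day part stands in a row labelled grade 3, and the grade 4 row does not refer to it. If that reading was intended, the proposed line simply confirms it.

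A second reply is that the difference may be deliberate, because grade 4 has its own steroid regimen and a larger dose cut. The compatibility of the taper with a 21-day limit does not prove an oversight. Still, no reason is given for the longer window, and the dose cut settles the dose after a restart, not whether a slow-recovering patient should restart.

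A third reply is that much protection remains. This stands in full: hold, recovery to grade 1 or less, the 8-week limit, the second-occurrence stop, and the investigator's power to end treatment (4.2.3.1, 4.5.1). It is why the point is minor.

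Three stronger readings are tempting, and the documents do not support them:

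- A reader might infer that patients can be re-dosed while a grade 4 skin event is unresolved. The general rule forbids it.
- A reader might infer that skin is the one toxicity whose 21-day limit lapses with rising grade. Nephritis (Table 10) and musculoskeletal events (Table 18) also have a 21-day resume condition at grade 2 that is absent at grades 3 and 4, so uniqueness cannot be claimed.
- A reader might infer from the list in 5.2.3 that grade 4 bullous dermatitis is to be expected. That entry gives no grade. It shows that the plan contemplates such a skin event, not how severe or frequent it is.

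**Conclusion.** The inconsistency is real and narrow. It concerns a first related grade 4 skin event, other than SJS/TEN and palmar-plantar erythrodysesthesia, in a patient still at 2.0 mg/kg. As written, such a patient may restart at 1.0 mg/kg after recovering as late as 56 to 84 days from onset. A grade 3 event on the same course must stop for good after 21 days. For the worse event, any earlier stop for slow recovery rests on the investigator's judgement alone.

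This assumes that each row of Table 9 governs its own grade, that the row's two-level reduction overrides the general same-dose restart, and that no other delay is already running when the event begins. Visit windows are ignored.

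At most 17 patients are treated, and the available text gives no frequency of grade 4 skin events, so no effect on event or discontinuation counts is claimed. The sample size and the ORR test do not change. This is a cheap improvement of low severity.

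**What to change.** In the grade 4 row of Table 9, add either a line directing that the event be managed as grade 3, or an explicit line to hold MGC018 and discontinue it if the event has not resolved to grade 1 or baseline within 21 days. Keep the two-level reduction and the stop after a second occurrence.

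The cost is one line at the next amendment, with no added visits or data. The downside is that a patient whose grade 4 skin event recovers after day 21 loses the option of re-treatment, as a grade 3 patient already does.
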